Return of First-phase Insulin Secretion in Type 2 Diabetes is
Associated With Depletion of Pancreas Lipid

Study Protocol & Statistical Analysis Plan

NCT03430310

Date of Last Protocol Approval: 12/13/2023

[name], Principal Investigator
University of Alabama at Birmingham
Birmingham, AL 35294

Methods

Participants and Study Design

Participants were AA and EA adults, determined by self-reported race, with T2D and were recruited based on the following: Inclusion criteria were diagnosis within the past 10 years; treated with diet, metformin, SGLT2-inhibitors, DPP-IV inhibitors, or GLP-1 RAs; adult men and women aged 35-65 yr; HbA1c \leq 8.0; and with a BMI of 25-50 kg/m². Exclusion criteria were a change in body weight of >5 kg in the past 6 months; use of glucocorticoids; and tobacco or recreational drug use. Medication was discontinued 1 week prior to baseline testing for metformin and SGLT2-inhibitors, and 4 weeks prior to testing for DPP-IV-inhibitors and GLP-1 receptor agonists. Fasting glucose was monitored throughout the study, and any patient who demonstrated fasting glucose >200 mg/dL on 3 consecutive days was returned to medication. Routine physical activity was recorded by questionnaire at screening, and all participants were asked to maintain their usual level of physical activity throughout the study.

The study design was a 12-week randomized clinical trial with two arms: carbohydrate restricted (CR) and higher carbohydrate (HC). Both diets were developed by a Registered Dietitian who met with the study participants weekly. Participants were given detailed instructions on daily meal plans. Groceries were delivered to each participant weekly by a local delivery service. Participants prepared their own meals and snacks, at an energy level calculated to be weight-maintaining, based on the instructions provided by the study dietitian. Participants reported their body weight to the dietitian weekly, and their diet prescription was altered if their weight changed by more than 1 kg. The CR diet was composed of ~9% energy from carbohydrate, 26% energy from protein, and 65% energy from fat, whereas the HC diet was

composed of ~55% energy from carbohydrate, 25% energy from protein, and 20% energy from fat. The UAB Institutional Review Board approved the study.

Procedures

At baseline and after 12 weeks of diet therapy, participants underwent a standard, 75 g oral glucose tolerance test (OGTT) and a hyperglycemic clamp. The OGTT was 3 hours in length, with blood sampled at -30, -15, -5, 10, 20, 30, 60, 90, 120, 150 and 180 min relative to the start of glucose ingestion for measurement of glucose, insulin, and C-peptide.

The clamp protocol involved three stages: a 30-min stage to evaluate first-phase beta-cell response, a 2-hour phase to evaluate insulin sensitivity, and a final, 30-min phase to evaluate maximal beta-cell response to arginine. The first phase was conducted by administering a bolus of glucose over 2 min at time zero followed by an intravenous administration of glucose (as D20) to achieve a blood glucose concentration 50 mg/dL above that morning's fasted glucose concentration (G + 50). Formulas were used based on the RISE protocol (18) to determine both the bolus amount [weight (kg) x 50 mg/dL x 1.1 / 180] and to estimate the glucose infusion rate [weight (kg) x 5 x 60 / 180]; this rate was adjusted as necessary to achieve G + 50. Blood was sampled at -20 and -5 min prior to the start of glucose administration; then at 2, 4, 6, 8, 10, 15, 20, 25, and 30 min after the start of glucose administration. Glucose was measured at bedside, and sera were stored for later assessment of glucose, insulin, and C-peptide. After the 30-min first-phase stage, blood glucose was brought to 200 mg/dL and maintained there for the next 2 hours to determine insulin sensitivity. During this time, blood was sampled every 5 minutes. After the 150-min blood sample was collected, a second bolus of D20 was administered over 2 min [weight (kg) x 100 mg/dL x 1.1 / 180]. Blood glucose was brought to 300 mg/dL and

maintained there with a variable infusion of D20. Blood was sampled every 5 minutes to minute 180. After the 180-min blood collection, 5 g arginine (10% in saline) was infused over 5 min. Blood was sampled every 2 min from 182 to 190 min to capture maximal C-peptide secretion.

Serum samples were stored at -70°C until analyzed. Glucose was measured on a SIRRUS chemistry analyzer (Stanbio Laboratory, Boerne, TX) using glucose oxidase reagent; the minimum detectable value was 2 mg/dl; inter-assay CV was 4.48%; and intra-assay CV was 1.28%. Insulin was assayed using immunofluorescence technology (TOSOH AIA900, TOSOH Bioscience, South San Francisco, CA); assay sensitivity was 0.5 uU/ml; inter-assay CV was 3.95% and intra-assay CV was 1.49%. C-peptide was analyzed on the TOSOH; assay sensitivity was 0.04 ng/ml; inter-assay CV was 6.81% and intra-assay CV was 1.67%.

For this study, the lipid content of pancreas and liver was be assessed by MRI using the 3-point Dixon approach. This method provides high-resolution contiguous images of the abdomen in breathhold durations and its intrinsic 3D imaging capability allows whole organs and spatial variations in ectopic fat across any region of the imaged anatomy to be evaluated. The 3-point M Dixon fat fraction (FF) is computed from the separated water and fat signals on a voxel-by-voxel basis. The accuracy of the fat fraction metric from this multi-echo fat quantification method has been validated in several pancreatic/hepatic fat quantification studies using the following equation: Fat fraction_{3-point M Dixon} = Signal Intensity_{(SI)FAT}/(_{(SI)WATER+SIFAT}) x 100%.

We will attempt to image both the head and tail of the pancreas, however all regions of the pancreas show similar associations with beta-cell function. Visceral fat volume also was assessed in a 10 cm region of interest. Trans-axial abdominal images was obtained using 3D volumetric T1-weighted magnetization prepared rapid acquisition gradient echo (MPRAGE).

The echo time, repetition time, and pulse flip angles will be selected to optimize the signal-intensity contrast between adipose and non-adipose tissue. Image acquisition was done at the Civitan International Neuroimaging Laboratory under the oversight of [name] using a state-of-the-art Prisma 3.0-Tesla whole-body MRI scanner. Image analysis was done by [name] using Slice-O-Matic software for visceral fat volume, and Osirix MD on an iMAC computer for assessing the signal intensity of a region of interest on the pancreas and liver to determine the fat fraction. By quantifying visceral adipose, and pancreatic and hepatic lipid, we will be able to examine whether these depots change in tandem during the intervention, and which depot is most closely associated with improvements in insulin sensitivity and beta-cell function.

Body composition: Body composition was assessed using dual-energy X-ray absorptiometry (DXA) in the Metabolism Core Laboratory of UAB's Nutrition Obesity Research Center (NORC) with a Lunar iDXA instrument (GE Healthcare, Madison, WI) with the enCORE 2011 v15 (sp2) software package. Total body fat mass and lean body mass (LBM) in kg, as well as total body %fat, was recorded.

Resting energy expenditure (REE) and substrate utilization (respiratory quotient, RQ): REE and RQ was determined in the NORC Core Laboratory by indirect calorimetry (TrueOne 2400, Parvo Medics, Sandy, UT). Participants were tested in the fasted (10h) condition following a 30-min supine rest.

Calculations

OGTT: Fasting values were determined from the average of the -30, -15, and -5 minute time points. The first-phase C-peptide index (CPI) was calculated as the difference in C-peptide from 0 to 30 minutes divided by the difference in serum glucose from 0 to 30 minutes ($[C\text{-peptide}_{30\text{min}} - C\text{-peptide}_{0\text{min}}] / [glucose_{30\text{min}} - glucose_{0\text{min}}]$). The Matsuda Insulin Sensitivity Index

(ISI) was used as a measure of whole-body insulin sensitivity due to its ability to capture both hepatic and skeletal muscle-derived insulin sensitivity. The Disposition Index (DI), an index of beta-cell function, was calculated as the product of C-peptide secretion and insulin sensitivity, as reported: $DI = CPI \times ISI$.

Hyperglycemic clamp: The RISE protocol was used to calculate first-phase C-peptide response as the mean incremental response above baseline over minutes 2-10, and the maximal C-peptide response as the mean incremental response during minutes 184-190 above the mean at min 170-180. Insulin sensitivity was calculated as described for the hyperglycemic clamp.

Statistics:

a. *Analyses*. The primary analysis for each aim will be a mixed model, using all available data and utilizing the estimated correlation between measurement times. The mixed model is less biased towards statistically significant results in the context of missing data, and/or when a moderate to high correlation exists between outcome measures. For Aim 1, the primary outcome will be pancreas lipid. Statistical models will include time, diet, and the time-by-diet interaction. Other potential covariates (e.g., gender, race, total body fat, adherence to diet) will be explored in preliminary analyses. Similar analyses will be conducted for hepatic lipid and visceral adipose tissue. For Aim 2, the primary outcome will be beta-cell function, as reflected in first phase C-peptide secretion from the hyperglycemic clamp. Statistical models will include time, diet, and the time-by-diet interaction. Other potential covariates (e.g., gender, race, total body fat, adherence to diet, insulin sensitivity) will be explored in preliminary analyses. Similar analyses will be conducted for PhiD from the MMTT, and insulin sensitivity from the hyperglycemic clamp. Food records will be coded to assess adherence as a dichotomous variable, and adherence

will be defined as +/- 10 percentage points of the targeted carbohydrate intake. For Aim 3, the primary variable of interest is the race-by-diet interaction term, which will be added to the models from Aims 1 and 2. If either of these interaction terms is significant, the data will be analyzed separately within each race group. Influential data points and outliers will be examined in a sensitivity analyses.

Correlative analyses will be conducted between changes (week 12 minus baseline) in measures of glucose metabolism (e.g., glucose AUC from liquid meal test, HbA1c), markers of inflammation, visceral fat, and hepatic/pancreatic lipid with Pearson's correlations coefficients (adjusting for relevant confounding variables). The correlation between change in pancreas lipid and change in first-phase C-peptide secretion will be examined, adjusting for insulin sensitivity. For all analyses, variables known to deviate from a normal distribution will be log transformed.

All statistical tests will be two-sided and will be performed using an alpha level of 0.05.

Statistical analyses will be performed using SAS Version 9.4®. Baseline descriptive characteristics will summarized as means (SD) or proportions to include demographic, clinical, and other measures.

b. Power calculation. Based on our published data, a sample size of 15 in each group will have 80% power to detect a difference in means of -89.700 (the difference between a Group 1 mean, μ_1 , of 6.400 and a Group 2 mean, μ_2 , of 96.100) in first-phase response at week 12 assuming that the common standard deviation is 84.639 using a two group t-test with a 0.050 two-sided significance level. Because we believe that the association between pancreas lipid and beta-cell function will be stronger in African-Americans, we have elected to target a final sample size of

15 participants per diet-race group (total of 60 participants with complete data). Using the Fisher r-to-z transformation, a value of z can be calculated that can be applied to assess the significance of the difference between two correlation coefficients, r_a and r_b , found in two independent samples. Given 30 subjects in each race group, we will be able to detect a difference of 0.3 with a one-sided alpha of 0.05. We will recruit 80 participants (20 per diet-race group) to account for missing data, potential drop-outs, or for participants who have to withdraw from the study due to problems with glycemic control.

c. Randomization

The study statistician ([name]) will prepare a closed envelope randomization for the two treatment arms stratified by race group using Proc Plan in SAS Ver. 9.4®. Patients will receive their group assignment following baseline testing.

Patient management following the study:

[figure not shown]
Given that patients were removed from medication prior to study initiation, and were carefully monitored for glycemic control during the study, it is important to ensure that they make a smooth transition to a free-living situation. Following final testing, all study participants will be given access to continued diet/nutrition support, provided by the study team, to assure a smooth transition to a free-living diet. Patients will be able to choose their preferred diet (they may choose to stay on their assigned intervention diet, or to transition to a different diet).

Medical management, including of medication type and dosage, will be available during this transition. All patients will demonstrate stable glycemic control on a given diet and medication regimen before exiting the study.

[figure not shown]
Supplementary Table 1. Insulin sensitivity from the hyperglycemic clamp and OGTT (Matsuda Index) by race and diet.

Insulin sensitivity measure	Baseline Mean (SD)	Week 12 Mean (SD)	Change Mean (SEM)	P for change
Hyperglycemic clamp				
EA HC	9.13 (7.42)	15.87 (16.65)	5.31 (4.17)	0.24
EA CR	6.33 (5.74)	9.03 (6.06)	2.3 (2.74)	0.42
AA HC	6.65 (4.49)	8.12 (4.77)	1.28 (0.72)	0.09
AA CR	10.24 (8.99)	12.16 (19.96)	4.07 (3.42)	0.26
Matsuda Index (OGTT)				
EA HC	2.46 (1.91)	3.36 (2.27)	0.89 (0.49)	0.1
EA CR	2.08 (1.02)	2.74 (1.35)	0.66 (1)	0.083
AA HC	2.18 (1.16)	5.99 (2.98)	0.66 (0.32)	0.06
AA CR	3.11 (3.99)	4.39 (2.94)	1.28 (0.75)	0.11

Abbreviations: EA: European American, AA: African American, CR: Carbohydrate restricted diet, HC: Higher carbohydrate diet.

Supplementary Fig. 1. Schematic of the hyperglycemic clamp. Glucose is injected as a bolus over 2 minutes at 0 and 150 minutes. Arginine is infused from 180-185 minutes. After the time 0 bolus, blood glucose is brought to 50 mg/dL above basal and held there until minute 30 using an infusion of 20% dextrose. After the time 150 bolus, blood glucose is brought to 300 mg/dL and held there until minute 180 using an infusion of 20% dextrose. Data from a representative participant are shown at baseline (open circles) and 12 weeks (filled squares).

Supplementary Fig 2. CONSORT diagram.

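### Aims 1 and 2 name no tested diet contrast and leave the baseline diet difference free although diet is assigned after baseline; every contrast available is valid, but a baseline-adjusted one is generally more precise

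*Combined protocol and SAP*

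**What the plan says.** Under Statistics, a. Analyses, the plan states: "The primary analysis for each aim will be a mixed model, using all available data and utilizing the estimated correlation between measurement times". For Aim 1 (pancreas lipid) and again for Aim 2 (first-phase C-peptide from the clamp) it adds: "Statistical models will include time, diet, and the time-by-diet interaction". Further covariates, race among them, are only to be explored. The baseline value of the outcome is not listed, and no constraint on the baseline means is stated.

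Aim 3 is handled differently: "For Aim 3, the primary variable of interest is the race-by-diet interaction term", with this follow-up: "If either of these interaction terms is significant, the data will be analyzed separately within each race group".

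Under c. Randomization, allocation is stratified by race and "Patients will receive their group assignment following baseline testing".

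Under b. Power calculation, the 80% is for a difference "in first-phase response at week 12 assuming that the common standard deviation is 84.639 using a two group t-test" with 15 in each group. The target is 60 completers, 15 in each diet-by-race cell, so 30 per diet.

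**The concern.** The listed terms define a model but not a hypothesis. With two visits, three diet contrasts can be read from it:

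- **Time-by-diet.** With complete data, this is the raw difference between arms in mean change.
- **Diet difference at week 12.** With complete data, this is the raw difference in week-12 means, and the baseline value plays no part.
- **Diet main effect averaged over both visits.** Since the expected baseline difference is zero, this estimates half the week-12 effect.

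The plan undertakes to use the correlation between visits. With complete data none of the three point estimates does so. Time-by-diet gives baseline a fixed weight of one, and the week-12 contrast gives it none. The cause is the free diet main effect, which spends information on a baseline difference that randomisation after baseline has already set to zero in expectation. ANCOVA, or a mixed model with a common baseline mean, puts the estimated correlation to work.

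Two things are at stake: precision that could be had from data already collected, and a power figure that belongs to one of several possible tests.

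**Working it through.** **Inputs from the documents (Power calculation):** difference 89.7, SD 84.639, two-sided alpha 0.05, 15 per group; 30 completers per diet when the races are pooled.

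**Assumed, because the documents do not give them for the primary outcomes:** rho, the correlation between baseline and week 12; and k = baseline SD / week-12 SD. Supplementary Table 1 was not used to set them. It covers insulin sensitivity only, gives no cell sizes, and has rows that do not agree with themselves. For example, the Matsuda row for AA HC reports a change of 0.66 while its means differ by 5.99 − 2.18 = 3.81.

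**Step 1: reproduce the plan's figure.** Standardised difference 89.7/84.639 = 1.060. SE = 84.639 × √(2/15) = 30.91. Noncentral t power on 28 df is 80.0%, as stated. At 30 per diet the same test has 98.1%.

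**Step 2: formulas.** Let S = 84.639 × √(2/n), with n per group.
- Week 12: SE = S.
- Time-by-diet: SE = S × √(1 + k² − 2·rho·k).
- Averaged diet effect: effect 89.7/2 = 44.85; SE = S × √(1 + k² + 2·rho·k)/2.
- Baseline-adjusted: SE = S × √[(1 − rho²)(1 + 1/(2n − 4))], on 2n − 3 df. The last factor is 1 + 1/26 = 1.0385 at n = 15 and is the price of estimating the slope.

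Example, rho 0.3, k = 1, n = 15: time-by-diet SE = 30.91 × √1.4 = 36.57; adjusted SE = 30.91 × √(0.91 × 1.0385) = 30.04.

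**Step 3: power at 15 per group, k = 1.**

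| rho | Time-by-diet | Week 12 | Averaged diet effect | Baseline-adjusted |
|---|---|---|---|---|
| 0 | 51% | 80% | 51% | 78% |
| 0.3 | 66% | 80% | 41% | 82% |
| 0.5 | 80% | 80% | 37% | 89% |
| 0.7 | 95% | 80% | 33% | 97% |

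At rho 0.3/0.5/0.7 the adjusted variance is 0.675/0.779/0.883 of the time-by-diet variance and 0.945/0.779/0.530 of the week-12 variance.

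**Step 4: power at 30 per diet.** With k = 1, time-by-diet has 81% at rho 0 and 93/98/99.9% at rho 0.3/0.5/0.7. With k = 1.3 it has 69/83/93% at rho 0/0.3/0.5, while the adjusted contrast has 97.9/98.7/99.6%.

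**Step 5: where adjustment does not help.** In large samples the time-by-diet variance exceeds the adjusted variance by (k − rho)², in units of S², so the gain vanishes when rho is near k. At 15 per group, adjustment is slightly less precise than time-by-diet for rho of about 0.65 to 0.89 at k = 0.8, and above about 0.93 at k = 1. At k = 0.45 the variance ratios at rho 0.3/0.5/0.7 are 1.013/1.035/0.925. Against week 12, the break-even is (1 − rho²) × 1.0385 = 1, that is rho of about 0.19. The largest penalty in either case is the factor 1.0385, about 4% of variance.

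**Step 6: validity.** In simulated trials at 15 per group with no diet effect, all four tests rejected in 4.8 to 5.1% of trials. With a true difference of 89.7, the time-by-diet, week-12 and adjusted estimates centred on that value, and the averaged effect centred on half of it.

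**The case against.** The best reply is that this is a standard and valid model, that most readers would take time-by-diet as the intended test, and that the main comparison is not in trouble. Much of that stands. With 30 per diet, k = 1 and rho not negative, time-by-diet has at least 81% power for the stated difference. Where k = 1, a shortfall from 80% arises only in the within-race analyses at 15 per group, which are run only after a significant race-by-diet term. The reassurance for the pooled comparison does depend on k, as the k = 1.3 figures show. The presumption in favour of time-by-diet is reasonable, but the text does not state it. If it is granted, the only power figure for a diet effect belongs to a different test.

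Three further points are fair. First, the Power calculation already says plainly that its 80% is for an unadjusted week-12 t-test at 15 per group; what is missing is the link to the mixed model. Second, the argument that the correlation goes unused is about complete data. The plan allows for drop-out (80 recruited for 60 completers), and with missing week-12 values the mixed model does draw on the correlation. Third, every power figure here concerns first-phase C-peptide; the documents give no inputs for pancreas lipid.

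A reader might infer that the free diet main effect biases the result or inflates false positives. It does neither: allocation is random and all the contrasts hold their level.

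**Conclusion.** The point holds as one of precision and pre-specification. The plan names a tested term for Aim 3 but none for Aims 1 and 2, and the three contrasts its model can yield differ widely in power: at 15 per group, k = 1 and rho 0.5, from 37% for the averaged effect to 80% for the other two. Adjusting for baseline raises that to 89%. It costs at most about 4% of variance at 15 per group where it does not help.

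The size rests on assumed values of rho and k, so the gain should be called general, not certain. A reader might also conclude that the trial is underpowered or that its 80% is wrong. The documents support neither: the 80% reproduces exactly for the test it describes, and the pooled comparison has twice that sample size per diet.

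**What to change.** Name the tested contrast for both primary outcomes: the week-12 diet difference adjusted for baseline. Two models deliver it:

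- ANCOVA of week 12 on baseline, diet and race. Aim 3 then keeps its race-by-diet term.
- A common-baseline mixed model with time and time-by-diet, no diet main effect, an unstructured covariance, and race included. Aim 3 must then be tested by race-by-time-by-diet, with race and race-by-time in the model, because adding race-by-diet alone would let a baseline diet difference back in.

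Race belongs in either model as a committed term because randomisation is stratified by it.

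In the Power calculation, leave the existing statement and add that the analysis contrast differs from the t-test, with its power over a range of rho and k (on the log scale if the outcome is to be log transformed).

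The cost is one estimated slope, revised model wording including Aim 3, and a short table; no patients or measurements are added. The Methods are largely written in the past tense and Supplementary Table 1 already reports week-12 results for insulin sensitivity, so the change must be declared as an amendment or the adjusted model reported as a sensitivity analysis.

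### The Aim 1 and Aim 2 diet models may admit diet adherence and on-study body fat or insulin sensitivity, which could bias the diet effect by an unknown amount and in an unknown direction

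*Combined protocol and SAP*

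**What the plan says.** Statistics, part a (Analyses), names a mixed model as the primary analysis for each aim, with time, diet and time-by-diet as its fixed terms. Further covariates follow.

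- Aim 1 (pancreas lipid): "Other potential covariates (e.g., gender, race, total body fat, adherence to diet) will be explored in preliminary analyses".
- Aim 2 (first-phase C-peptide): "Other potential covariates (e.g., gender, race, total body fat, adherence to diet, insulin sensitivity) will be explored in preliminary analyses".
- Directly after the Aim 2 list: "Similar analyses will be conducted for PhiD from the MMTT, and insulin sensitivity from the hyperglycemic clamp". Insulin sensitivity is thus both a candidate covariate and an outcome of diet.
- Adherence is a yes/no variable coded from food records. It "will be defined as +/- 10 percentage points of the targeted carbohydrate intake".
- Aim 3 tests "the race-by-diet interaction term, which will be added to the models from Aims 1 and 2", so it inherits whatever those models contain.

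No sentence limits these covariates to baseline values, gives a rule for keeping or dropping them, or reserves the model without them as the main result.

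**The concern.** Randomisation protects the diet comparison only when the model conditions on things fixed before assignment. A variable that diet can change, or that is defined by the assigned diet, can take part of the diet effect into its own coefficient or create a difference where none exists.

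Adherence is such a variable by construction. Insulin sensitivity is one if the week-12 value is used, and so is body fat if a later scan is used. The models affected are the primary ones for Aims 1 and 2 and, through them, Aim 3. Because exploration has no stated rule, the reported diet effect could also depend on which covariates were kept after looking at the data.

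**Working it through.** **1. When each candidate is measured**

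- *Adherence.* Under Participants and Study Design, "The CR diet was composed of ~9% energy from carbohydrate"; the HC target is about 55%. A window of 10 points either side gives 9 ± 10, or about 0–19%, in CR, and 45–65% in HC. Only too much carbohydrate can fail a CR participant, whereas an HC participant can fail in either direction. Under Randomization, assignment follows baseline testing, so adherence cannot exist before it.
- *Insulin sensitivity.* It comes from the clamp, done at baseline and at week 12 (Procedures).
- *Total body fat.* It comes from DXA, with no visit stated. Diets were set "at an energy level calculated to be weight-maintaining", which limits a shift in body fat but does not exclude one. I give no size for it.

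**2. The plan's own figure**

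Power calculation: difference 89.7, SD 84.639, 15 per group, two-sided 0.05. The effect is 89.7/84.639 = 1.06 SD. The noncentrality is 1.06 × √(15/2) = 2.90 on 28 degrees of freedom, giving power 0.800. The stated 80% is reproduced. It refers to an unadjusted two-group comparison at week 12.

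**3. On-study insulin sensitivity (Aim 2)**

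Let *shift* be the diet effect on the change in sensitivity (in SD), and *slope* the within-arm coefficient of the outcome on sensitivity (in SD). Then

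adjusted time-by-diet = total effect − shift × slope.

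The shifts and slopes below are assumptions.

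| Shift | Slope | Adjusted time-by-diet (total 1.06) |
|---|---|---|
| 0.3 | 0.2 | 1.06 − 0.06 = 1.00 |
| 0.5 | 0.3 | 1.06 − 0.15 = 0.91 |
| 0.8 | 0.5 | 1.06 − 0.40 = 0.66 |
| 0.3 | −0.2 | 1.06 + 0.06 = 1.12 |
| 0.5 | −0.3 | 1.06 + 0.15 = 1.21 |
| 0.8 | −0.5 | 1.06 + 0.40 = 1.46 |
| 0 | 0.5 | 1.06 |

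A baseline value of sensitivity leaves 1.06 unchanged. A separate two-visit simulation with 30 per arm, shift 0.5 and slope 0.5 moved time-by-diet from 0.52 to 0.27, as the formula predicts.

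*Direction from Supplementary Table 1* (clamp, Change column, CR minus HC):

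- EA: 2.30 − 5.31 = −3.01, SE √(4.17² + 2.74²) = 4.99.
- AA: 4.07 − 1.28 = +2.79, SE √(0.72² + 3.42²) = 3.49.
- Average: −0.11, SE ½√(4.99² + 3.49²) = 3.05.
- Baseline SD, pooled with equal weights: √[(7.42² + 5.74² + 4.49² + 8.99²)/4] = 6.87.

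In SD units, with normal-approximation 95% intervals, this is −0.44 in EA (−1.86 to 0.98), +0.41 in AA (−0.59 to 1.40) and −0.02 on average (−0.88 to 0.85). At slope 0.5 the average moves time-by-diet by +0.01 SD, and the interval limits move it by −0.43 to +0.44.

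The Change column does not equal the difference of the column means; different numbers of participants per column could explain this. From the column means, EA is (9.03 − 6.33) − (15.87 − 9.13) = −4.04 and AA is (12.16 − 10.24) − (8.12 − 6.65) = +0.45. The average is −1.80, or −0.26 SD, which moves time-by-diet by +0.13 SD at slope 0.5. Either way the direction is open.

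**4. Adherence (Aims 1 and 2)**

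The documents give no adherence by arm. Assume 85% in HC and 60% in CR, no true diet effect, and a normally distributed trait behind adherence that correlates 0.3–0.5 with the outcome.

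If the trait acts equally at both visits, the pooled within-arm slope on adherence is r × [φ(1.036) + φ(0.253)] / [0.85 × 0.15 + 0.60 × 0.40] = r × 0.620/0.3675 = 1.69r. The false CR minus HC difference is 0.25 × 1.69r, which is 0.13 at r = 0.3 and 0.21 at r = 0.5.

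Two-visit generalised least squares with unstructured covariance, on 1,000,000 simulated participants per case, gave:

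- *Adherence main effect, complete data.* Time-by-diet is unchanged. The false arm difference is the same at baseline and week 12: 0.13–0.21 SD if the trait acts at both visits, and 0.07–0.13 SD if at week 12 only.
- *Main effect, 25% of week-12 values missing at random* (20 recruited for 15 complete). Time-by-diet moves by at most 0.001 SD.
- *Adherence-by-time term.* Time-by-diet is biased by 0.13–0.21 SD if the trait acts only at week 12, and by 0 if it acts equally at both visits.
- *Other gaps.* With 75% in both arms there is no bias. Reversing the gap reverses the sign.
- *Dropout of 15% if adherent and 51% if not* (25% overall). Time-by-diet bias is 0.01–0.05 SD without adherence in the model and −0.01 to 0.04 SD with it.

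**The case against.** The strongest reply is that the plan commits to nothing. Its fixed terms are the right ones, and the rest are only candidates for exploration. That is true, so the harm is possible rather than certain. Exploration without a rule, feeding a primary model that nothing protects, is still the gap.

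Second, the one covariate that is certainly post-randomisation does least to the key term. An adherence main effect leaves time-by-diet unchanged, and the bias in that term needs an adherence-by-time interaction that the plan does not mention. With adherence-related dropout, leaving adherence out does no better. This stands for time-by-diet. It does not cover the week-12 contrast, which is what the power calculation targets. It may not cover Aim 3 either, where race-by-diet is stated without a time component: if the adherence gap differed by race, a main effect alone could shift that term, by an amount the documents cannot give. The false difference at baseline would at least be a visible warning, since no diet had then been given.

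Third, judging secretion against concurrent sensitivity is a legitimate question. In Calculations, "The Disposition Index (DI), an index of beta-cell function, was calculated as the product of C-peptide secretion and insulin sensitivity", and a separate correlation is adjusted for sensitivity. Agreed, but that is a different question from the effect of diet on secretion, and the plan does not label it as such inside the diet model.

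Fourth, the estimated shift in sensitivity averages near zero. The interval excludes little and the race groups point in opposite directions, so this neither confirms nor removes the risk. For total body fat, the weight-maintaining design makes a large shift less likely, and no size is claimed.

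**Conclusion.** The concern holds. The plan permits post-randomisation covariates in its primary diet models: adherence for certain, and body fat and (Aim 2) insulin sensitivity because no baseline limit is set. Neither the size nor the direction of any bias can be fixed from the documents.

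The most consequential case is on-study insulin sensitivity in Aim 2, where assumed shifts of 0.3–0.8 SD and slopes of 0.2–0.5 turn a 1.06 SD effect into anything from 0.66 to 1.46. For Aim 1 the exposure is smaller. With the adherence rates assumed here, it is a false arm difference of 0.07–0.21 SD at each visit, or a time-by-diet bias of about 0.13–0.21 SD if an adherence-by-time term is added and the trait acts only at week 12. There is no bias if diet does not move the covariate, if adherence is equal between arms, or if only pre-randomisation values are used.

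**What to change.** State that the primary model for Aims 1 and 2 contains time, diet and time-by-diet, and that any further covariate must be measured before randomisation; race, the stratification factor, may be included. Keep adherence, on-study insulin sensitivity and on-study body fat out of that model and of the Aim 3 models built on it. Report them in secondary analyses labelled for what they answer: adherence or per-protocol, mediation, or secretion relative to sensitivity.

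Supplementary Table 1 already shows week-12 results. Where results exist, present the model without post-randomisation covariates as the main result, and do not describe a covariate list fixed now as pre-specified.

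The cost is wording and the output of one model. An adherence- or sensitivity-adjusted result can then no longer be primary. If dropout depends on adherence, the unadjusted model can carry a small time-by-diet bias (0.01–0.05 SD above), so keep the adherence model as a labelled sensitivity analysis.
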